# **Protection against Risks:**

We will follow safeguards to minimize the risk to our subjects: a) we will carefully monitor response to medical treatment every 2 weeks by telephone contact and during clinic visits, b) women of reproductive age who are sexually active will undergo a urine pregnancy tests prior to participation in the study, c) female subjects whom are pregnant, breast-feeding, or not willing to use appropriate contraception at time of enrollment will not be included in the study, d) patients with significant comorbidities such as chronic kidney disease > stage III, liver cirrhosis, gastroparesis, and pancreatic disorders will be excluded from the study.

Patients will receive diabetes education prior to discharge and will be instructed on hypoglycemia sign/symptoms and treatment. Patients will be asked to call the diabetes center and/or PCP in the event of hypoglycemia. If a patient develops hypoglycemia, the dose of insulin will be reduced (see treatment algorithm).

# **Statistical Analysis:**

This pilot study will compare treatment irregularities (insulin omission, mistiming and dosing) between Insulclock versus conventional insulin injection pen device. We will also compare differences in glycemic control, as measured by change in mean HbA1c from baseline, number of hypoglycemic events, percentage of subjects maintaining therapy, 7-point SMBG profile, fasting plasma (FPG) profile, and HRQoL assessments (Patient reported outcomes) between groups.

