# **Secondary Objectives:**

To demonstrate non-inferiority of Insulclock compared with standard insulin pen device on:

[figure not shown]
- Treatment satisfaction -Diabetes Treatment Satisfaction Questionnaire Status (DTSQs)
- Diabetes Related Quality of Life (DRQoL)
- Adherence:
  - Frequency of insulin irregularities (omission, mistiming and dosing)
- Glycemic control:
  - Glycemic control, as measure by change in mean HbA1c from baseline
  - Frequency of hypoglycemia
  - o 7-point SMBG profile
  - Daily fasting glucose profile

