### **Study Visits**

Screening (Visit 1)

Approximately 1-2 weeks prior to the start of the study, all potential study patients will be screened to check their eligibility after signing the informed consent form (ICF) and assigned a patient identification number. Medical history, physical examination, height, weight, vital signs, pre-existing conditions, and concomitant medications will be recorded during this visit. Laboratory assessments performed at Visit 1 to determine eligibility for the study include pregnancy tests for females, and HbA1c, serum chemistry, assays. Patients who do not meet all the inclusion criteria at Visit 1 will be considered screen failures and will not be randomized to participate in the study.

Eligible patients will be trained on the use of the glucometer to monitor their BG levels. Patients will be given diabetes diaries and associated training to record all glucose levels, insulin doses, and episodes of hypoglycemia.

Insulin administration technique will be reviewed prior to randomization to ensure good technique. Reinforcement will be provided as needed during the follow-up visits.

Only eligible patients treated with a once daily insulin dose of NPH, detemir, glargine insulin will be switched to SoloSTAR pen (glargine U100) at a total dose (TDD).

Antidiabetic agents will be continued at the same dose, except insulin secretagogues which can be stopped if HbA1c is <8% or reduced by half if HbA1c is >8%.

Patients will be instructed in performing glucose testing at home before meals, with a minimum of 2 out of the 4 pre-meal and bedtime glucose measurements per day. In addition, patients must perform a 7-point SMBG (fasting, before meals, 2 hours after meals, and bedtime) done between 3 to 5 days prior to Visit 2.

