# Instructions to be provided to Patients in Preparation for Visit 2 (Randomization visit)

- All patients will be instructed to provide daily glucose records. In addition, they will perform a 7-point SMBG done between 3 to 5 days prior to Visit 2.
- Insulclock usage, compliance, and technique will be reviewed.
- Patients who complied with the 7-point glucose testing (fasting, before meals, 2 hours after meals, and bedtime) and fulfill the eligibility criteria at Visit 2 will be randomized to participate in the study.
- Diabetes Treatment Satisfaction Questionnaire Status (DTSQs)

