# Interim Visits (visit 5 and 11)

The following activities occur during interim visits:

- Patients will receive detailed instruction on the use of the Insulclock system
- Study diaries will be collected and reviewed for BG levels, episodes of hypoglycemia, insulin selfadministration
- Dose of glargine insulin will be adjusted as needed (page 8).
- Patients will be instructed in performing glucose testing at home before meals, with a minimum of 2 out of the 4 pre-meal and bedtime glucose measurements per day.

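### The 7-point SMBG profile is a secondary outcome, but the plan requests it only once, before randomisation, so the profile as defined cannot be compared between feedback and no feedback

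*Combined protocol and SAP*

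**What the plan says.** The Secondary Objectives open with "To demonstrate non-inferiority of Insulclock compared with standard insulin pen device on" and, under glycemic control, list the "7-point SMBG profile". The Statistical Analysis section repeats it among the outcomes to be compared between groups: "percentage of subjects maintaining therapy, 7-point SMBG profile, fasting plasma (FPG) profile".

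The measurement is requested in two places, and both describe the same occasion. The screening part of Study Visits requires a "7-point SMBG (fasting, before meals, 2 hours after meals, and bedtime) done between 3 to 5 days prior to Visit 2". The instructions in preparation for Visit 2 say that "they will perform a 7-point SMBG done between 3 to 5 days prior to Visit 2", and make compliance with it a condition of being randomised. Visit 2 is the randomisation visit.

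From Visit 2 onward the home-testing instruction is lighter. At Visit 2 and at interim Visits 5 and 11, patients test before meals "with a minimum of 2 out of the 4 pre-meal and bedtime glucose measurements per day".

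**The concern.** An outcome that is to be compared between two conditions has to be measured under both. Here the only requested profile precedes either condition. It can describe the patients at entry, but it carries no information about feedback versus no feedback.

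If sites follow the text, a named secondary outcome reaches the analysis without its on-treatment measurement. The loss is permanent, because post-meal values that were not taken cannot be recovered from diaries or the device afterwards.

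**Working it through.** **1. The plan's own figure for this class of outcome.** Power Considerations claims over 80% power for continuous secondary outcomes, at a difference of 0.41 SD, alpha 0.05 and within-subject correlation 0.3, using a paired t-test. The inputs are 40 per group, so 80 patients, and 15% attrition.
- Pairs: 80 × 0.85 = 68.
- SD of the within-patient difference: √(2 × (1 − 0.3)) = 1.183 SD.
- Standardised effect: 0.41 / 1.183 = 0.347.
- Power with 68 pairs, two-sided (sidedness is not stated, so this is an assumption): 80.4%.

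The claim reproduces. It rests on each of the 68 completers having a value under each condition. (Selection of Patients gives a total of 150 rather than 80. The count of scheduled profiles below does not depend on which is right.)

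**2. Where a 7-point profile is requested.**

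| Section | Glucose measurement requested | 7-point profile |
|---|---|---|
| Study Visits, screening | Daily home testing, plus a profile before Visit 2 | Yes, before randomisation |
| Preparation for Visit 2 | The same profile, as an entry condition | Same occasion |
| Randomization (Visit 2) | At least 2 of 4 pre-meal and bedtime readings a day | No |
| Telephone Visits | None listed | No |
| Interim Visits (5 and 11) | At least 2 of 4 pre-meal and bedtime readings a day; diary review | No |
| Crossover visit (Visit 8) | HbA1c; diary review | No |
| Visit 14 (End of Study) | HbA1c; diary review | No |
| Assessment of Results | HbA1c and fasting glucose averages | No |

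The count is one before randomisation, none in period 1 and none in period 2.

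**3. What the analysis needs.** For continuous secondary outcomes, Analysis of Secondary Endpoints contrasts period 2 with period 1. Each patient therefore needs one value per period. The schedule yields 0 pairs for this outcome, against the 68 assumed in step 1. That section also leaves the 7-point profile out of the secondary endpoints it names, so the outcome has no analysis of its own.

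**4. Whether routine testing can stand in.** Taking three meals a day and counting the fasting value as the first pre-meal reading, the profile has 3 pre-meal + 3 post-meal + 1 bedtime = 7 points. Routine testing covers the pre-meal and bedtime points, 3 + 1 = 4, and requires only 2 of them on any day. The remaining 7 − 4 = 3 points, all 2 hours after meals, are not requested at any time after randomisation.

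**The case against.** The best defence is that the visit lists are not exhaustive. The quality-of-life questionnaires are absent from them too, yet they are plainly intended, and the telephone-visit section lists no activities at all. A missing line could be a drafting slip. This has some force, but Assessment of Results supplies the questionnaire timing (baseline, weeks 12 and 24) and the HbA1c and fasting-glucose timing, and it gives nothing for the 7-point profile. The reviewed text has no schedule-of-assessments table, and a figure next to the Secondary Objectives is not shown. The finding is therefore limited to what the text requests.

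A second defence is that a reader might infer that the comparison has no data at all, and the documents do not support that. Patients are told to record all their glucose readings, diaries are reviewed at Visits 5, 8, 11 and 14, and two readings a day is a floor rather than a ceiling. Averaged over days, up to four pre-meal and bedtime points could be formed in each period, and any voluntary post-meal readings would also be in the diary. That part of the defence stands. But such a profile is partial, is pieced together from different days, and depends for its post-meal part on who chose to test. It is not the 7-point profile the protocol defines.

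Third, the stakes are modest. Glycemic control is an exploratory aim in a self-described pilot, and HbA1c and fasting averages are scheduled. This limits the weight of the point but does not remove it.

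**Conclusion.** The point holds. In the text as supplied, the 7-point profile is promised as a between-condition comparison but is requested once before randomisation and not at all in either treatment period. The three post-meal points are never requested on treatment, so the profile as defined cannot be compared between feedback and no feedback.

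It would go too far to conclude that glycemic control as a whole cannot be assessed. HbA1c and fasting averages have scheduled on-treatment values, and the diaries may give a partial profile. The primary adherence endpoint and its power are unaffected.

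The conclusion assumes that no schedule table outside the reviewed text adds a profile, and that sites collect what the visit text asks for. The size is one secondary outcome. It is worth correcting before data collection because the omission cannot be repaired later. The missing non-inferiority margin is a separate problem that this correction does not solve.

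**What to change.** Request the same 7-point SMBG at the end of each period: in the days before Visit 8, completed before the patient switches condition, and again before Visit 14. Add one line to each of those two visit lists and to Assessment of Results.

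Reconcile the crossover timing first, because the crossover-visit section gives both week 12 and week 14. If these are two counting origins for the same day, nothing is lost. If the switch really comes at week 12 and the visit at week 14, a profile taken 3 to 5 days before the visit would fall 14 − 5 = 9 to 14 − 3 = 11 days into the second condition and would be credited to the wrong one.

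Name one summary measure, for example the mean of the seven points. Add it to Analysis of Secondary Endpoints and compare it within patient across periods by the method already given there.

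The cost is two days of seven finger-sticks per patient, 2 × 7 = 14 readings, on meters and training already provided. Some of these replace readings that patients would take anyway.

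If the sponsor does not want this burden, delete the 7-point profile from the Secondary Objectives and from Statistical Analysis, and keep the pre-randomisation profile as an entry check only.

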### Analysis of Primary Endpoint:

The primary outcome of treatment adherence with the use of Insulclock with feedback or no information (blinded) is whether a patient has a good adherent to the treatment regimen (assessed based on insulin omission, mistiming, and dosing). Given the 2 by 2 cross-over design, the superiority of the Insulclock system over the conventional insulin pen device will be determined by comparing the percent of patients showing a good treatment adherence with Insulclock but a poor treatment adherence with the conventional device to the percent of patients showing a poor treatment adherence with Insulclock but a good treatment adherence with the conventional device. We will perform this comparison based on McNemar's test assuming the period effect is negligible. We will further conduct logistic regression to accommodate potential period effect and adjust for other potential confounders. We will apply standard model selection and model checking procedures (such as the Hosmer-Lemeshow tests) to decide and evaluate the final model. A p value of <0.05 will be considered significant.

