# **Assessment of Results:**

The primary outcome of *treatment adherence* with the use of Insulclock with feedback or no feedback information (blinded) will be determined by the percentage of patients and number of insulin omission, mistiming and dosing. Number insulin irregularities will be registered on the Insulclock device and data will be retrieved during each clinic visit.

**For treatment satisfaction**, subjects' responses to questions 1, 7 and 8 of the DTSQc will be used. A comparison of the score on the DTSQs from week 12 to week 24 as well as using the score on the other questions of the DTSQc, which would overcome the ceiling limitation of using the DTSQs by itself, will also be used to assess treatment satisfaction . The Diabetes Treatment Satisfaction Questionnaire Status (DTSQs) form will be administered at weeks 0, 12 and 24.

Questionnaires will be given at week 0 for standardization purposes. The amplitude of the score on the DTSQc gives the degree of change in satisfaction while the direction (positive or negative) will provide guidance on the preference of one device over the other (i.e., if we predict that patients greatly prefer alarm reminders over nothing and he/she started the group 1 with daily reminders then transitioned to group 2 without the daily reminders, his/her score would be '-3', whereas if he/she was initially not getting the daily reminders followed by the daily reminders then the score would be '+3').

**Ouality of life** will be assessed at baseline and again at weeks 12 and 24 in order to determine the impact of the type of therapy on this outcome. Patients will be given the Diabetes Quality of Life Clinical Trial Questionnaire-Revised (DQLCTQ-R), the Problem Areas In Diabetes scale (PAID) and the Elderly Diabetes Burden Scale (EDBS) at baseline, weeks 12 and 24 to assess their quality of life and any potential impact of the treatment regimen .

*Glycemic Control* will be assessed via HbA1c at weeks -1, 12 and 24 and via fasting blood glucose averages at weeks 0, 12 and 24 from point of care testing during the preceding week.

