### **Power Considerations**

This is a pilot study and we plan to recruit 40 subjects for each study group. Our power calculation is mainly based on the binary primary outcome. We assume no more than 15% attrition rate, and assume no period

effect. In the following table, we give the power for detecting the superiority of Insulclock based on Exact Test for Binomial proportion with alpha=0.05, under different projections for the proportion of subjects showing treatment preference (i.e. adherent under one treatment but not under the other), denoted by Ptp, and projections for the probability of preference to Insulclock given showing treatment preference, denoted by p.

	P tp					
Power		90%	80%	70%	60%	50%
р	0.6	31.2%	28.2%	21.5%	17.8%	13.9%
	0.7	87.9%	83.7%	74.9%	66.5%	55.4%
	0.8	>99%	>99%	>99%	97.6%	93.8%
	0.9	>99%	>99%	>99%	>99%	>99%

Regarding the secondary outcomes, the power calculations can be made conservatively based on superiority hypotheses without specifying the equivalent margins. For continuous secondary outcomes, we would have over 80% power to detect outcome difference of 0.41 times the standard deviation based on paired t tests, with alpha=0.05, assuming equal outcome standard deviations for Insulclock and the conventional device, and within subject correlation equal to 0.3.

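### The primary test replaces about 84 device-recorded doses per patient and period with one good/poor label, leaves the number of irregularities without a stated analysis, and loses material power unless the effect is large.

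*Combined protocol and SAP*

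**What the plan says.** Under Analysis of Primary Endpoint, the outcome "is whether a patient has a good adherent to the treatment regimen", judged from omission, mistiming and dosing. No cut-off for good adherence is given. Superiority is to be judged by "comparing the percent of patients showing a good treatment adherence with Insulclock but a poor treatment adherence with the conventional device" with the percentage showing the reverse pattern. On the test, the section says: "We will perform this comparison based on McNemar's test assuming the period effect is negligible". A logistic regression follows, allowing for period and other covariates, but it uses the same label. Power Considerations adds: "Our power calculation is mainly based on the binary primary outcome".

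Other sections describe a count. Under Assessment of Results, "Number insulin irregularities will be registered on the Insulclock device", and the primary outcome is described there both as a percentage of patients and as a number of irregularities. The opening of Statistical Analysis states: "This pilot study will compare treatment irregularities (insulin omission, mistiming and dosing"). Aim 1 compares irregularities at each clinic visit. Secondary Objectives list the frequency of irregularities, under a non-inferiority heading. Analysis of Secondary Endpoints gives general methods for continuous outcomes but does not name irregularities among its endpoints.

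Under Methods, all patients use the device in both periods, with or without feedback, so dose-level data exist under both conditions.

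**The concern.** A 12-week period of once-daily dosing gives 12 × 7 = 84 scheduled doses, so each patient has a finely graded irregularity proportion in each period. The primary test keeps one bit of it. A patient who goes from 40% to 22% irregular doses, or from 15% to 3%, may keep the same label and add nothing to the test. Fixing the cut-off in advance, which the plan also needs, does not restore this information, and neither does a logistic regression on the label.

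The risk is that a moderate effect of feedback is missed by the test that decides the trial while it is visible in data already collected.

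**Working it through.** **1. The plan's own figures.** Power Considerations says "we plan to recruit 40 subjects for each study group", with at most 15% attrition: 80 × 0.85 = 68 completers. (Study Schedule also gives 80 randomised; Selection of Patients gives 150. I use 80, which reproduces the table.) The stated test is the "Exact Test for Binomial proportion with alpha=0.05". With m = 68 × P_tp discordant patients, m = 61, 54, 48, 41 and 34. At m = 61 the two-sided exact test rejects at 22 or fewer, or 39 or more, and power at p = 0.7 is 87.9%. The rest of that row comes to 83.7%, 74.9%, 66.5% and 55.4%. The rows for p = 0.6 and 0.8 also match. The table is right for its test.

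For continuous secondary outcomes the plan gives 0.41 SD and within-subject correlation 0.3. The standardised paired difference is 0.41/√(2 × (1 − 0.3)) = 0.41/1.183 = 0.347. The noncentrality is 0.347 × √68 = 2.86, against a critical t of 1.996 on 67 degrees of freedom. Power is 80.4%, matching the plan's claim of over 80%.

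**2. The same values applied to adherence.** This is an assumption, because the plan states them for secondary outcomes only. Take a bivariate normal adherence score with shift 0.41 and correlation 0.3, cut so that a given share of patients is good on the comparator. McNemar power is exact and averaged over the random number of discordant patients.

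| Good on comparator | Discordant (P_tp) | Towards Insulclock (p) | Power, label | Power, uncut score |
|---|---|---|---|---|
| 20% | 34% | 0.70 | 40% | 80% |
| 33% | 41% | 0.69 | 46% | 80% |
| 50% | 41% | 0.69 | 46% | 80% |
| 70% | 31% | 0.70 | 38% | 80% |

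Over shifts of 0.3 to 0.5 SD and correlations of 0 to 0.7, the ratio of label power to uncut power runs from 0.34 to 0.84.

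**3. Dose-level simulation.** All inputs here are assumed: 68 patients, 84 doses per period, mean irregular rate without feedback of 14%, 21% or 31%, between-patient log-odds SD 1.0, and cut-offs of 80% or 90% regular doses. Repeat runs differ by a few points.

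| Odds ratio for an irregular dose | Within-patient period SD (log-odds) | Exact McNemar on label | Paired t-test on rate |
|---|---|---|---|
| 0.67 | 0.4–0.7 | 28–62% | 73–99% |
| 0.67 | 1.0 | 18–26% | 43–54% |
| 0.5 | 0.4–0.7 | 68–98% | 99–100% |

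At odds ratio 0.67 with SD 0.4–0.7, only about 15–30% of patients are discordant, below the plan's projected 50–90%. Comparing period differences between sequences gives the same power as the paired t-test. With no effect, the rate tests reject in 4–6% of trials and exact McNemar in 1–4%, so part of the gap is the conservatism of the exact form used in the power section.

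**4. The plan's own table cells.** With a normal score and a symmetric cut that reproduces each cell, the ratio of label power to uncut power is 0.53–0.66 at p = 0.6, 0.69–0.90 at p = 0.7 and 0.94–1.00 at p = 0.8.

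**The case against.** The strongest objection is to the size. A reader might infer that the label always halves power. The documents give no irregularity rate, SD, correlation, cut-off or effect for adherence, so no fixed loss follows from them, and at odds ratio 0.5 or p of 0.8 and above the label does well. This stands: the loss must be stated with its assumptions and as a range.

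The moderate-effect simulations also have far fewer discordant patients than the plan projects, and McNemar power depends on that number. This stands as a disclosure. It does not remove the concern: the plan's own 0.41 SD and 0.3 correlation imply 31–41% discordant in the normal model, below every column of the table. Discordance far above half is also hard to square with a patient's two periods being positively related. Non-negative correlation requires P_tp ≤ 1/(1 + 2√(p(1 − p))), which at p = 0.7 is 1/(1 + 2√0.21) = 52%.

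A reader might infer that the plan discards the counts. It does not: they are recorded and named in several sections. What is missing is a stated analysis, and the role of the count in the primary conclusion.

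Finally, a responder measure is easy to interpret, and a mean shift driven by slightly late doses could be significant without more patients becoming adherent. This is a fair reason to keep the label as supportive and to report the irregularity types separately.

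**Conclusion.** The point holds conditionally. The plan decides its primary question on one label per patient and period, although its own description of the outcome includes the number of irregularities and the device supplies it. For moderate effects the loss is material: about 80% against 38–46% with the plan's continuous planning values borrowed for adherence, and about 73–99% against 28–62% at an assumed odds ratio of 0.67 with within-patient SD 0.4–0.7. With more within-patient variation (SD 1.0) both tests are weak and the gain is about 20–35 points. For large effects the loss is small to moderate.

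It should not be read as an error in the power table, which reproduces. The direction of the loss is the same throughout the scenarios examined; its size is not established by the documents. The study calls itself a pilot, which makes an estimate with an interval more useful than a test of label changes.

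**What to change.** In Analysis of Primary Endpoint:

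- Define the primary measure as each patient's proportion of scheduled doses in a period that were irregular: omitted, mistimed, or wrongly dosed relative to the dose prescribed at that time. The last clause is needed because titration allows dose changes every 3 days. Fix all definitions before unblinding.
- Compare the period 2 minus period 1 difference between the two randomised sequences with a two-sample t-test. Report the estimated treatment difference (half the between-sequence contrast) with its 95% CI, and use the rank-sum test as a sensitivity analysis. A period effect common to both sequences then cancels.
- Keep the good/poor McNemar comparison as supportive, with a pre-specified cut-off, and report the three irregularity types separately.

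In Power Considerations, add power for the rate with its assumed SD, correlation and effect, and keep the existing table for the supportive analysis.

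The cost is new wording in these two sections plus working definitions of mistiming and dosing error, which the label needs anyway. The real downside is that the headline becomes a mean difference in irregular doses rather than a percentage of patients, and weights the three irregularity types equally.
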